Anatomical variation of femoral nerve location in relation to femoral artery -
An ultrasonographic evaluation

Date: 20th March 2016

Anatomical variation of femoral nerve location in relation to femoral artery - An ultrasonographic evaluation

Introduction:

The femoral nerve block is ideal for surgeries of the femur, knee, or anterior thigh and is often combined with a sciatic nerve block for near complete lower extremity analgesia. The classic teaching is that the femoral nerve lies lateral to femoral artery sandwiched between the fascia iliaca and iliopsoas muscle¹.

Aim:

The objective of the study is to find out the anatomical variation in the site of the femoral nerve in relation to the femoral artery, with respect to the age, sex, and BMI of the patient.

Anatomy:

The femoral nerve is the largest branch of lumbar plexus originating from ventral rami of 2nd, 3rd and 4th lumbar nerves. The nerve descends through the psoas muscle emerging from psoas at lower part of the lateral border. It passes underneath the inguinal ligament lying in the concave groove between iliacus and psoas muscle under fascia iliaca ². At the inguinal crease, it lies 0.5-1 cm lateral to the femoral artery ^{1,3,4}. It divides into anterior and posterior divisions and supplies iliacus, pectineus and muscles of anterior compartment of thigh except tensor fascia lata, and cutaneous innervation to the anterior and medial part of thigh and medial side of the leg. It also supplies articular branches to hip and knee joint.

Sonoanatomy:

The femoral nerve is scanned with high frequency linear probe because of its superficial nature. Distal to the inguinal ligament, it lies lateral to femoral artery deep to fascia iliaca. The artery can be easily identified because of its pulsation and if there is difficulty Doppler can be used. The femoral nerve can be seen as a triangular hyperechoic shadow lateral to the artery². Routinely, distal to the inguinal crease, when the femoral artery bifurcates into the superficial femoral artery and profunda femoris artery, the femoral nerve too divides into an anterior and posterior division. Occasionally, the bifurcation of the artery occurs early, even as high as the inguinal crease ^{5,6}.

Methodology:

200 patients above the age of 18 coming for fixation of fracture femur, will be enrolled in the study after explanation of the details. They will be divided into two groups according to age.

Group 1 - age between 18 and 60 and Group 2 - age above 60.

Those persons below the age group of 18, patients with any neurological illness that hinders them from giving a valid consent and those with local pathology at the inguinal region will be excluded. Those scans in which measurement is not possible secondary to poor image quality is excluded after enrolment. Those patients in which there is abnormal anatomy of femoral nerve or artery like early division (above the inguinal ligament) also not included in the study.

After explaining the scanning procedure in detail and after ensuring the privacy, inguinal region will be exposed. Scanning will be done by same anaesthesiologist in all the patients. High frequency linear probe of frequency 5-16 Hz of Sonosite X-porte (Fujifilm Sonosite, Inc. Bothell, Wa98021 USA) will be used for scanning and saving image.

The probe is placed on the inguinal crease with pointer facing laterally and the femoral artery is identified by its pulsation. The nerve is identified as a hyper echoic triangular shadow lateral to the femoral artery. If the nerve is not visualised clearly, the probe is adjusted by tilting to get a clear image of the femoral nerve. Once a clear image is obtained, the image will be saved per the patient enrolment number.

A vertical line is drawn from the medial end of the femoral nerve. Another horizontal line is drawn from the 9o'clock position of femoral artery perpendicular to the first line. The distance between the points where the two lines meet and the 9o'clock position of the femoral artery is measured. (fig1)

Fig 1 : measuring horizontal distance

If the femoral artery is branching at the level of inguinal crease, the scanning is done proximally to find out the point where the artery is single. The measurement will be taken at this point.

In addition, the data will be analyzed with respect to the sex, and BMI of the patient to know whether these variables influence the position of the femoral nerve in relation to the femoral artery.

Statistical method:

Pearson Correlation was used to find the correlation between age, BMI and distance between femoral artery & nerve. Independent t-test was used to compare the distance value by age group and gender.

References:

1. Hadzic A (2012) Femoral nerve block. In Hadzic A (ed) Hadzics's peripheral nerve blocks and anatomy for ultrasound guided regional anesthesia , 2nd edn. McGraw-Hill, Newyork, pp 267-279.

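### The open-ended exclusion of abnormal anatomy allows patients to be dropped for unusual nerve position, which is the outcome, and no account of those left out is planned

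*Combined protocol and SAP*

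**What the plan says.** The Aim section sets out to "find out the anatomical variation in the site of the femoral nerve in relation to the femoral artery", with respect to age, sex and BMI. The Methodology section then gives these rules:

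- **Number:** "200 patients above the age of 18 coming for fixation of fracture femur, will be enrolled in the study".
- **Image exclusion:** "Those scans in which measurement is not possible secondary to poor image quality is excluded after enrolment".
- **Anatomy exclusion:** patients with "abnormal anatomy of femoral nerve or artery like early division (above the inguinal ligament) also not included in the study".
- **Branching at the inguinal crease:** kept. In that case "the scanning is done proximally to find out the point where the artery is single", and the distance is measured there.
- **Finding the nerve:** "The nerve is identified as a hyper echoic triangular shadow lateral to the femoral artery".
- **Operator:** "Scanning will be done by same anaesthesiologist in all the patients".

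The Statistical method section contains Pearson correlations of age and BMI with the measured distance, and independent t-tests of distance by age group and by gender. It says nothing about patients without a distance.

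**The concern.** A study of variation should not be free to remove the unusual cases. The anatomy exclusion names one example and no closed list, and it covers the nerve as well as the artery. A nerve lying over or medial to the artery could be classed as abnormal anatomy. Since the protocol looks for the nerve on the lateral side, it could also end up as a scan that cannot be measured. In either case the patient would leave the study without trace.

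Two things are at stake. The spread of positions among analysed patients could be narrower than among the patients scanned. And a reader could not tell how many scanned patients were removed, for what reason, or whether they differed in age, sex or BMI from those who remained.

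**Working it through.** The point rests on the text, so the check is mainly to set the rules side by side.

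**1. Is the excluded class closed?** No. The exclusion is introduced by the word *like*, followed by one example. No definition or list appears elsewhere in the document.

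**2. When, and by whom, is it applied?** The document describes no imaging before the study scan, and one anaesthesiologist does all the scans. The exclusion would therefore in practice be decided from the scan that yields the distance, by the person who obtains it. This is an inference; the text does not state the timing.

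**3. Which part has a measurement reason?** The crease rule shows that the distance is meant to be taken where the artery is single. An artery that has divided above the ligament may offer no such point, so leaving it out of the distance analysis is reasonable. That reason concerns the artery. It gives no ground for excluding on nerve position, and no ground for leaving the omitted patients uncounted.

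**4. Does the measurement rule itself remove unusual positions?** Not necessarily. The distance runs horizontally from the 9 o'clock point of the artery to a vertical line through the medial end of the nerve. That can be drawn when the nerve is close to the artery or overlaps it, although the sign of the result in the overlapping case is not stated.

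**5. Is anyone left out accounted for?** The Methodology and Statistical method sections plan no count, description, replacement or flow account. Image saving is described only for the point at which a clear image has been obtained, so excluded scans may not be recoverable later.

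**6. What does 200 mean?** Patients are enrolled to 200, poor scans leave after enrolment, and patients with abnormal anatomy are described as not included. Whether the last group counts towards the 200 is not stated. The document gives no loss rate. For assumed combined losses of 5%, 10% and 20%:

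| Assumed loss | Measured, if 200 are scanned | Scanned, if 200 must be measured |
|---|---|---|
| 5% | 200 × 0.95 = 190 | 200 / 0.95 = 210.5, so 211 |
| 10% | 200 × 0.90 = 180 | 200 / 0.90 = 222.2, so 223 |
| 20% | 200 × 0.80 = 160 | 200 / 0.80 = 250 |

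**7. How much could the spread shrink? (hypothetical only)** Suppose distance is normal and the lowest fraction p is removed by a sharp cut. With a = Φ⁻¹(p) and λ = φ(a)/(1 − p), the SD kept, as a share of the true SD, is √(1 + aλ − λ²).

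- For p = 0.10: a = −1.2816, φ(a) = 0.1755 and λ = 0.1950. The variance is 1 − 0.2499 − 0.0380 = 0.712, so the SD is 0.844 of its true value.
- For p = 0.02: a = −2.0537, φ(a) = 0.0484 and λ = 0.0494. The variance is 1 − 0.1015 − 0.0024 = 0.896, so the SD is 0.947 of its true value.

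Under weak selection instead (odds of loss doubling per SD of distance), simulation gives 0.980 at 10% loss and 0.995 at 2%. Nothing in the document says that small distances are the ones lost, or at what rate. These figures show only that the effect could range from negligible to appreciable.

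**The case against.** The strongest reply is that the only example of abnormal anatomy is a branching anomaly. The protocol nowhere calls an unusual nerve position abnormal, and its measurement construction can handle a nerve close to or over the artery. On this view, selection on the outcome is conjecture. It is right that the text does not require such selection. What stands against the reply is that an undefined class, judged on the outcome scan, does not prevent it.

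The reply also says that the plan keeps more than it seems to. This is correct. The Sonoanatomy section mentions arterial bifurcation as high as the crease, and that variant is retained and measured more proximally. Only division above the ligament is named for exclusion, and there the lack of a single-artery reference point is a fair reason.

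Finally, the planned analyses are correlations and t-tests on distance, and the study is not a prevalence survey of anomalies. This limits the point but does not remove it. Those analyses still rest on whoever is left after an undefined exclusion, and the stated aim is variation.

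A reader might infer three stronger things, none of which the documents support:

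- **That patients with a non-lateral nerve will be excluded.** The wording allows it but does not say it. A non-lateral nerve could also be missed through the identification rule alone.
- **That the study will report a falsely low proportion of unusual positions.** No such proportion is planned.
- **That the BMI correlation will be biased.** No passage links image quality or abnormal anatomy to BMI, so any figure for that effect would rest on invented inputs.

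**Conclusion.** The point holds as a flaw in the exclusion rule, together with a gap in accounting for patients. Followed as written, the rule can cut off part of the quantity under study, and a reader would be unable to see whether it had. The size of any understatement cannot be estimated, because the documents give no loss rate and no link between loss and distance. The SD figures above are hypothetical and should not be read as predictions. What is firm is that the class is undefined, no account of those left out is planned, and the meaning of 200 is open.

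The conclusion assumes that abnormal anatomy is recognised on the study scan. If some patients were instead excluded on the basis of earlier imaging, the risk of selection on the outcome would be smaller for them, but the missing count would remain. The change should be made. It bears directly on the aim and is cheap, but with bias of unknown size it does not put the whole study in doubt.

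**What to change.** 1. In the Methodology section, limit the anatomy exclusion to division above the inguinal ligament. State that nerve position relative to the artery is never a reason for exclusion.
2. For every scanned patient with no measurable distance, record the reason at the scan: early arterial division, early nerve division or poor image. Where the nerve is visible, also record whether it was lateral, overlapping or medial.
3. In the Statistical method section, plan a table of the number and percentage of scanned patients left out, by reason, with their age, sex and BMI beside those of the patients analysed. State whether 200 means scanned or measured.

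The cost is protocol wording, one field on the data sheet and one table, with no extra scans and no change to the planned tests. The downside is that a few patients contribute a category but no distance.

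### The plan describes one distance per patient and no repeat reading; re-reading the saved images would cheaply reduce and quantify line-placement error, whose size the documents do not give

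*Combined protocol and SAP*

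**What the plan says.** The Aim is to "find out the anatomical variation in the site of the femoral nerve in relation to the femoral artery", considered by age, sex and BMI. Under Anatomy, the only figure on the scale of the distance is "At the inguinal crease, it lies 0.5-1 cm lateral to the femoral artery". No SD is given anywhere.

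Under Methodology, "200 patients above the age of 18 coming for fixation of fracture femur, will be enrolled". On who does the work: "Scanning will be done by same anaesthesiologist in all the patients". If the nerve is unclear, "the probe is adjusted by tilting to get a clear image of the femoral nerve". Then "Once a clear image is obtained, the image will be saved per the patient enrolment number". Two lines are drawn, one from the nerve's medial edge and one from the artery's 9 o'clock point, and "The distance between the points where the two lines meet and the 9o'clock position of the femoral artery is measured".

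The text does not mention a second reading, averaging, a within-reader SD, an intraclass correlation (ICC) or masking of the reader. It does not say how many readings are made, or whether the person who scans also draws the lines. Under Statistical method, the distance goes straight into Pearson correlations with age and BMI and into t-tests by age group and sex.

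**The concern.** The variance of the recorded distances is the variance between patients plus the variance of the measurement. If each image is read once, nothing in the data separates the two. Placing a line at the edge of a bright triangular shadow takes judgement, and the distances of interest are a few millimetres.

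Three consequences follow if the error is random and unrelated to age, sex and BMI:

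- the reported spread is wider than the true spread;
- both correlations are pulled toward zero, so a null result for age or BMI is harder to interpret;
- the t-tests lose power, although their mean differences are not biased.

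Using one scanner removes differences between scanners. It does not remove the variation of one reader from one reading to the next.

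**Working it through.** **Inputs.** From the documents: n = 200, taken as all analysed, although some scans may be excluded after enrolment. The plan derives no power or sample size, so there is no figure of its own to reproduce. Assumed: two-sided 5% level; true between-patient SD s = 2 mm; reading-error SD e = 0.5, 1 or 2 mm; true correlation 0.20, with 0.30 as a check; error unrelated to age, sex and BMI; no error other than reading error.

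**Formulas.**

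- Reliability, one reading: R = s²/(s² + e²). Mean of two: R₂ = s²/(s² + e²/2).
- Observed correlation = true correlation × √R (or √R₂).
- Observed SD, one reading = √(s² + e²).
- Power = Φ(atanh(r) × √(n − 3) − 1.96), with r the observed correlation.

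**No error.** atanh(0.20) = 0.2027 and √197 = 14.04. The product is 2.845; less 1.96 this is 0.885, so power is 81.2%. The smallest correlation detectable with 80% power is 0.197, so a true 0.20 has almost no slack.

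**True correlation 0.20, s = 2 mm.**

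| e (mm) | R, one reading | Observed r | Observed SD (mm) | Power, one reading | R₂, mean of two | Power, mean of two |
|---|---|---|---|---|---|---|
| 0.5 | 0.94 | 0.194 | 2.06 | 78.8% | 0.97 | 80.0% |
| 1 | 0.80 | 0.179 | 2.24 | 71.8% | 0.89 | 76.4% |
| 2 | 0.50 | 0.141 | 2.83 | 51.5% | 0.67 | 63.8% |

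Simulation (8,000 runs, n = 200) agrees: 81.3% with no error and 71.5% at R = 0.8.

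**Sensitivity to the assumed SD.** If 0.5-1 cm is taken to span about 4 SD, then s = 5/4 = 1.25 mm. Errors of 0.25, 0.5 and 1 mm then give R = 0.96, 0.86 and 0.61, and correlations shrink to 98%, 93% and 78% of their true value. With s = 2.5 mm the same errors leave 99.5%, 98% and 93%.

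**Sensitivity to the true correlation.** At 0.30, power is 99.1% with no error, 97.1% at R = 0.8 and 91.3% at R = 0.6. In the extreme case R = 0.5, r = 0.30 × √0.5 = 0.212 and power is 86%.

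**t-tests.** For a standardised difference of 0.4 with an assumed 100 per group, power is 80.7% without error, 76.5% at R = 0.9 and 71.6% at R = 0.8.

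**Correcting the spread.** The variance of two-reading means is s² + e²/2, so the amount to subtract is half the within-reader variance. With s = 2 and e = 2 it is 4 + 2 = 6; subtracting 2 returns an SD of 2 mm. Subtracting the full 4 would give √2 = 1.41 mm, which is too small.

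**What re-reading cannot see.** Take s = 1.25 mm, reading error 0.5 mm and error from probe level and tilt 1.0 mm. The variances are 1.5625, 0.25 and 1.0, total 2.8125. Two readings of the same image would show an ICC of (1.5625 + 1.0)/2.8125 = 0.91, while the reliability for anatomy is 1.5625/2.8125 = 0.56.

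**The case against.** The strongest reply is that the size is unknown and may be trivial. At 0.5 mm the second reading raises power from 78.8% to 80.0%. The 2 mm case sets reading error equal to all the true variation between patients, with nothing in the documents to support it. A true correlation of 0.20 lies at the detection threshold, where attenuation shows most. All of this stands.

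The plan also limits error: fixed landmarks, a probe adjusted until the nerve is clear, and exclusion of scans too poor to measure. These help, but they do not yield an estimate of the error that remains. The planned analyses are correlations and t-tests, and no anatomical SD is listed as an estimate. That is fair, though the Aim is framed as variation, so a spread is likely to be reported and read as anatomy.

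To report reliability alone, about 40 re-read images would do: the 95% interval for the error SD runs from about 0.82 to 1.28 times the estimate, against 0.91 to 1.11 with all 200. That also stands, but only re-reading every image allows the mean of two to be analysed throughout.

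A reader might infer three stronger things that the documents do not support:

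- **That the plan fixes a single reading by the scanning anaesthesiologist.** The quoted sentence concerns scanning only. One reading is the plain sense of the text, but it is inferred from silence, and the reader is not identified.
- **That reading error is known to be large enough to explain a null result.** No error figure is given. A distance of 5-10 mm does not settle it, because reliability depends on the spread between patients, not on the mean.
- **That re-reading would isolate anatomical variation.** Error from probe level and tilt is already in the saved image and would remain, as would any constant bias of the reader.

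**Conclusion.** The point holds as a cheap improvement. The plan describes one distance from one saved image and provides no way to estimate or reduce reading error.

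For a weak true correlation of 0.20 and a true SD of 2 mm, the loss of power ranges from about 2 percentage points (error 0.5 mm) through 9 (1 mm) to 30 (2 mm). The mean of two readings recovers about 1, 5 and 12 points of this. For a true correlation of 0.30 the loss is much smaller. The documents cannot say where in this range the study lies; without replicate readings, its own data could not say either.

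The direction of the effect rests on random error unrelated to age, sex and BMI. If the reader knows these and is influenced by them, a correlation could shift either way, and averaging would not cure it. This is why masking belongs in the fix.

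**What to change.** State in Methodology who draws the lines and how often, and add text such as:

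> One named reader measures each saved image twice, at least one week apart, in a new random order, masked to the first value and to age, sex and BMI. The mean of the two readings is analysed. The within-reader SD and ICC are reported. If a spread corrected for reading error is given, half the within-reader variance is subtracted from the variance of the two-reading means, and it is stated that error from probe level and tilt remains.

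The cost is about 200 extra readings of stored images by the same person, with no further staff, scan or patient contact. The limit is that it captures reading error only, so the ICC should be described as same-image, within-reader agreement.

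### The only outcome is a distance from hand-placed lines, and the plan does not say who places them, when, or whether that reader knows age, sex or BMI

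*Combined protocol and SAP*

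**What the plan says.** The Aim in the combined protocol and SAP is to describe where the femoral nerve lies relative to the femoral artery "with respect to the age, sex, and BMI of the patient". The explanatory variables are these three patient characteristics.

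Methodology describes two steps.

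- **Acquisition.** "Scanning will be done by same anaesthesiologist in all the patients". If the nerve is not clearly seen, "the probe is adjusted by tilting to get a clear image of the femoral nerve". Then: "Once a clear image is obtained, the image will be saved per the patient enrolment number".
- **Measurement.** "A vertical line is drawn from the medial end of the femoral nerve", and a horizontal line is taken from the artery's 9 o'clock position to meet it. "The distance between the points where the two lines meet and the 9o'clock position of the femoral artery is measured".

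One named role does the scanning. The measurement steps are in the passive and name nobody. The plan does not say whether the lines are placed at the bedside or later, what the reader knows about the patient, or whether any reading is repeated. Neither masking nor blinding is mentioned.

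Statistical method gives independent t-tests of the distance by age group and gender, and Pearson correlations of the distance with age and BMI.

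**The concern.** The medial end of a hyperechoic shadow is a judged landmark, so the distance depends partly on the reader. A reader error that is the same in every patient cancels out of a comparison. One that varies with age, sex or build does not: it goes straight into the difference or correlation being estimated, and neither the t-test nor the Pearson coefficient can tell it from anatomy.

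Using a single operator removes variation between operators but not this kind of error. If that operator is also the reader, that person has met the patient and can see sex and build and gauge age. Saving images by enrolment number does not mask the reading unless the reader is also kept from the patient data, and the plan does not say so.

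A significant result by age group, sex or BMI would then be open to the objection that it reflects line placement.

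**Working it through.** The plan gives no power calculation, so there is no figure of its own to reproduce. The check asks how often a t-test would be significant if the true difference were zero and the readings in one age group were shifted by *b*.

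**Inputs from the document**
- Methodology: "200 patients above the age of 18 coming for fixation of fracture femur, will be enrolled in the study", so N = 200.
- Methodology: "Group 1 - age between 18 and 60 and Group 2 - age above 60". The split is not stated.
- Anatomy: the expected distance is 0.5–1 cm, that is 5–10 mm. No SD is given.

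**Assumptions**
- Two-sided 5% test and true difference zero.
- Group split 100:100, with 160:40 as an uneven case.
- SD of the distance 1.5, 2, 3, 4 or 5 mm.
- Shift *b* of 0.25 or 0.5 mm. On a 5–10 mm distance, 0.5 mm is 5–10% (0.5/10 to 0.5/5).

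**Formulas**
- SE = SD × √(1/n₁ + 1/n₂)
- Noncentrality = *b*/SE, with 198 degrees of freedom and critical t = 1.972
- False-positive rate = P(|T| > 1.972) for T noncentral t
- Smallest significant observed difference = 1.972 × SE

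**Worked case** (SD 2 mm, 100:100, *b* = 0.5 mm)
- SE = 2 × √(0.01 + 0.01) = 0.283 mm
- Noncentrality = 0.5/0.283 = 1.77
- False-positive rate = 42%
- Smallest significant difference = 1.972 × 0.283 = 0.56 mm

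**Results**

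| SD (mm) | 100:100, 0.25 mm | 100:100, 0.5 mm | 160:40, 0.25 mm | 160:40, 0.5 mm |
|---|---|---|---|---|
| 1.5 | 22% | 65% | 16% | 47% |
| 2 | 14% | 42% | 11% | 29% |
| 3 | 9% | 22% | 8% | 16% |
| 4 | 7% | 14% | 6% | 11% |
| 5 | 6% | 11% | 6% | 9% |

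Every entry exceeds the nominal 5%. At 100:100 the smallest significant difference runs from 0.42 mm (SD 1.5 mm) to 1.39 mm (SD 5 mm).

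The comparison by sex follows the same arithmetic for a given split. For the correlations, the smallest significant coefficient is r = t/√(df + t²) = 1.972/√(198 + 3.889) = 0.139, and r² = 0.019. A trend explaining just under 2% of the variance in distance would therefore be significant at N = 200.

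If masking reduces *b* to zero, the rate from this source returns to the assumed 5%, with no change in N.

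**The case against.** The strongest reply is that this is silence rather than a stated flaw. The image is saved before the lines are described, which is compatible with a later reading by someone who never saw the patient. That stands as a reading of the text: a reader might infer that the person measuring is unmasked and can see age, sex and build, but the document does not establish it. What remains is that the plan also permits the unmasked route and gives no safeguard against it.

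A second reply is that the shifts are assumed. The Aim is exploratory and states no direction, so nothing in the document suggests which way a reader would lean. This stands too. The table shows sensitivity to a shift and is not evidence that one exists. At an SD of 4–5 mm a 0.25 mm shift barely moves the error rate.

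Two further inferences are tempting and fail.

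- **That the bias could never be corrected.** Because the images are kept, line-placement bias can be addressed later by a masked re-reading. Bias from probe adjustment and choice of frame cannot be.
- **That a masked reading would be complete.** Tissue depth on the image may hint at BMI, and the operator still sees the patient while acquiring the image.

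Finally, delaying measurement has a cost. Methodology excludes scans that cannot be measured because of poor image quality, and an unusable frame found late may be impossible to repeat. This stands, and the fix provides for it with a bedside check.

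**Conclusion.** The concern holds as a gap in the design. The plan leaves the reader, the timing and the reader's knowledge of the explanatory variables open for a subjective reading of its only outcome. It therefore permits a reading by the operator who saw every patient. It does not state that the reading is unmasked, and it gives no sign that a bias is present or in which direction it would act.

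The size is conditional. With a true difference of zero and a two-sided 5% test, a 0.5 mm shift gives a false-positive rate between 9% and 65% over the SDs and splits examined, and a 0.25 mm shift between 6% and 22%. The position within those ranges depends on an SD and a group split that the plan does not give. The change is worth making because the images are already to be saved and the safeguard costs little.

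**What to change.** Add to Methodology text to this effect:

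*At the bedside the operator confirms only that the saved image is measurable; no distance is taken. The distance is measured later on the saved images, relabelled with a random code and read in random order, without access to age, sex or BMI. Measurements are locked before they are merged with the patient data.*

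The text should also name who does the reading. The same anaesthesiologist may do it after a delay, provided the codes are shuffled.

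**Cost.** A short protocol addition and a shuffled code list. No extra patients, scans or staff are needed.

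**Downsides.** Measurements become available later. Image acquisition and frame choice stay unmasked, and tissue depth may still hint at BMI, so the report should describe the masking as partial. The bedside check limits the risk of finding an unmeasurable image too late to rescan.

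### The text gives the nerve–artery distance no sign, so a nerve whose medial end lies over the artery can be recorded like one lateral to it

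*Combined protocol and SAP*

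**What the plan says.** The Aim is to describe how the site of the femoral nerve varies relative to the femoral artery, by age, sex and BMI.

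Under Methodology, a vertical line is dropped through the medial end of the nerve and a horizontal line runs to it from the artery's 9 o'clock point. Then "The distance between the points where the two lines meet and the 9o'clock position of the femoral artery is measured". The sentence is followed by a reference to Fig 1.

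Four other statements bear on the point:

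- Orientation: "The probe is placed on the inguinal crease with pointer facing laterally". With the usual on-screen marker side, 9 o'clock is then the artery's lateral edge in either leg.
- Identification: "The nerve is identified as a hyper echoic triangular shadow lateral to the femoral artery". If the nerve is unclear, the probe is tilted until it is clear, and "Once a clear image is obtained, the image will be saved per the patient enrolment number".
- Exclusion: patients with "abnormal anatomy of femoral nerve or artery like early division (above the inguinal ligament) also not included in the study".
- Expected position (Anatomy): "At the inguinal crease, it lies 0.5-1 cm lateral to the femoral artery". No SD is given, and overlap is not mentioned.

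The distance goes directly into the analyses under Statistical method: "Pearson Correlation was used to find the correlation between age, BMI and distance between femoral artery & nerve", and t-tests by age group and gender.

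**The concern.** A distance between two points cannot be negative. If the nerve's medial end lies over or under the artery, it falls medial to the 9 o'clock point, and the rule as written still returns a positive number. The departures from the classic lateral position would then be mixed with ordinary values, in a study meant to describe variation in that position.

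The identification sentence adds to this, because it takes the lateral position as given. The anatomy exclusion offers early division only as an example, so someone applying it could take a wholly non-lateral nerve to be abnormal anatomy.

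At stake is chiefly the description: how many nerves are not clear of the artery. Overlap share is not a named endpoint, but it falls within the Aim, and neither a correlation nor a t-test on an unsigned distance would show it. A secondary effect is attenuation of those two analyses.

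**Working it through.** **No figure to reproduce.** The plan gives 200 patients without alpha, power, SD or effect size. Everything below except the 200 and the 0.5–1 cm position is an assumption.

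**Assumptions.** Signed distance x is normal with mean μ and SD σ. μ is 5, 7.5 or 10 mm (the 0.5–1 cm range and its midpoint), σ is 2–4 mm, and alpha is two-sided 0.05. Every overlapping nerve is measured and recorded as |x|.

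**Step 1: overlap share.** p = Φ(−μ/σ). At μ = 5, σ = 4: p = Φ(−1.25) = 10.6%, about 21 of 200.

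**Step 2: effect on the correlation.** For normal variables the covariance of age with |x| is ρσ(1 − 2p), so

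r(unsigned) = ρ(1 − 2p)σ / SD(|x|), where SD(|x|)² = μ² + σ² − m² and m = σ√(2/π)·exp(−μ²/2σ²) + μ(1 − 2p).

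At μ = 5, σ = 4: m = 5.405 and SD(|x|) = √(25 + 16 − 29.21) = 3.434. The factor is 0.789 × 4 / 3.434 = 0.919. A true ρ of 0.30 reads 0.276, and 0.20 reads 0.184. Simulation with 4,000,000 draws gives the same values.

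**Step 3: power at n = 200.** Φ(atanh(r)·√197 − 1.96).

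| μ = 5 mm, σ | Overlap (of 200) | ρ = 0.30 reads | Power (signed 99%) | ρ = 0.20 reads | Power (signed 81%) |
|---|---|---|---|---|---|
| 2 | 0.6% (1) | 0.299 | 99% | 0.200 | 81% |
| 2.5 | 2.3% (5) | 0.297 | 99% | 0.198 | 80% |
| 3 | 4.8% (10) | 0.292 | 99% | 0.194 | 79% |
| 4 | 10.6% (21) | 0.276 | 98% | 0.184 | 74% |

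Further out the effect is smaller. At μ = 7.5, overlap is 0.01–3.0% and r is 0.296 at worst. At μ = 10 it is at most 0.6%. If 0.5–1 cm is read as the spread of individuals (mean 7.5, SD 2.5), overlap is 0.1%.

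**Step 4: effect on a group difference.** Using m from Step 2, a true 7 versus 5 mm difference reads 1.99, 1.90 and 1.72 mm at σ = 2, 3 and 4. In a separate illustration with 100 per group and a true difference of 0.4 SD, signed power is 80.7%. With overlaps recorded as positive it is 80.5, 78.4, 74.4 and 60.4% at 1, 5, 10 and 20% overlap.

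**Step 5: is there a threshold?** At 20% overlap, a true correlation of 0.30 reads about 0.238 and power is still 92.6%. The 0.4 SD group difference falls to 60.4% power at the same overlap. The answer turns on the assumed effect, so the documents support no cut-off.

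**Step 6: nerves that could be missed at scanning.** These would lie wholly medial to 9 o'clock, i.e. x < −w for nerve width w (assumed 3–8 mm). At μ = 5, σ = 4, Φ(−(5 + w)/4) is 2.3, 0.6 and 0.06% for w = 3, 5 and 8. That is at most 5 of 200. At σ = 3 it is at most 0.4%.

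**The case against.** **The figure may settle it.** The measurement sentence points to Fig 1, which is not available here and cannot count as missing from the plan. It may carry a direction. This stands as a limit on the point, although a picture of a typical lateral nerve would not say how to record an overlapping one.

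**Overlapping nerves are not left out.** A reader might infer that the plan drops every overlapping nerve. The text does not support that. A nerve that overlaps the artery but extends laterally still fits the identification sentence and is measured from its medial end. Unclear views are dealt with by tilting, and scans are dropped after enrolment only for poor image quality. The anatomy exclusion gives a branching example, and using it against position would contradict the Aim. What remains is a possible misreading that concerns wholly non-lateral nerves, which are few under the assumptions in Step 6. I therefore give no results for excluding all overlaps.

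**The information is largely recoverable.** One anaesthesiologist scans every patient and the images are saved, so the sign can be re-read for every measured nerve. This stands, but it does not help with a nerve missed or excluded at scanning.

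**Lateral is a legitimate landmark.** The Anatomy and Sonoanatomy sections present it as the usual site, and nothing shows that appearance alone identifies the nerve reliably. This also stands, and the fix keeps the landmark.

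**Conclusion.** The point holds as a minor design improvement. In the supplied text the outcome is unsigned, so overlap can be recorded as ordinary lateral distance, and the description the Aim calls for would lose its most informative cases.

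A reader might go further and infer that the planned Pearson and t-test results are seriously biased, or that they become so above a particular overlap share. Neither follows. Over the assumed SDs of 2–4 mm at a mean of 5 mm, a correlation of 0.30 reads 0.299 to 0.276 and a 2 mm difference reads 1.99 to 1.72 mm. At larger means the effect on the correlation is smaller still. The effect grows with overlap, but the overlap rate, SD and effect size are all absent from the documents. Nor do the documents show that any distance was misrecorded; they show only that the wording allows it.

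**What to change.** 1. Define the distance as signed: positive when the nerve's medial end is lateral to the artery's lateral edge, zero at it, negative when medial to it. Use this value in the planned Pearson and t-test analyses. Read the sign from the saved images after confirming the on-screen marker side.
2. Amend the identification sentence to say that the nerve is usually lateral to the artery but is measured wherever it is seen deep to the fascia iliaca. Sonoanatomy already uses that landmark: "Distal to the inguinal ligament, it lies lateral to femoral artery deep to fascia iliaca".
3. State that a non-lateral position alone is not an abnormal-anatomy exclusion.
4. Report the number of nerves at or medial to the artery's lateral edge with a 95% CI (Wilson). With 200 measured, 10 such nerves would give 2.7–9.0%. None would give an upper limit of 3.84/203.84 = 1.9%, a statement an unsigned distance cannot support.

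The cost is three wording changes, one sign per image and one extra proportion to report, with no further scans, staff or patients. If scanning is already finished, only items 1 and 4 apply, and only to nerves that were measured.
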